6.5.6. Electrocardiograms

Centrally read ECG variables will be summarized by mean change from baseline to each measurement time for heart rate, PR interval, RR interval, QRS width, QT interval and QTcB (Bazett's correction) and QTcF (Fridericia's correction) values. Additionally, the incidence of categorical increases in QTc intervals will be provided. Categories for QTcF and QTcB are ≥ 450 msec, ≥ 480 msec, and ≥ 500 msec. Categories for QTcF and QTcB as change from baseline are ≥ 30 msec increase, ≥ 60 msec increase and ≥ 75 msec increase. QTcF is considered the primary QTc value as this correction is more appropriate.

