4.2. Exclusion Criteria

Subjects with any of the following characteristics/conditions will not be included in the study:

1. Any subjects from the preceding double blind trial who experienced a serious adverse event which required study medication to be discontinued and the subject to be withdrawn from the study. Subjects who experienced cardiac arrhythmias, conduction abnormalities, or QTc prolongation (confirmed and persistent Fridericia's correction (QTcF) >480 msec or increase from baseline QTcF >60 msec) during the preceding study.
2. Subjects requiring any medications not allowed by the Concomitant Medication [Table 12](#) (see “[Concomitant Treatment\(s\)](#)”).
3. Subjects who require treatment with drugs that are known to consistently prolong the QT interval (see Concomitant Medication [Table 12](#)).
4. Subjects who are judged by the investigator as being at imminent risk of suicide.
5. Subjects living in the same home as another study participant or having the same caregiver during the same enrollment period (Such subjects can be enrolled in the study at different times but may not be in the study at the same time).
6. Subjects should be excluded or a risk assessment should be done to verify that it is safe for the subject to participate in the trial if the subject's responses on the C-SSRS or other information based on the investigator's judgment indicate:
 - Suicide ideation associated with actual intent and a method or plan such that a positive response ('Yes') is made on items 4 or 5 of the suicidal ideation subscale of the C-SSRS; or
 - Any suicide behaviors such that a determination of 'yes' is made to any of the suicide behavior items of the C-SSRS.
7. Pregnant female subjects, breastfeeding female subjects.
8. Participation in other studies other than the preceding Study.
9. Other acute or chronic medical or psychiatric condition including recent (within the past year) or active suicidal ideation or behavior or laboratory abnormality that may increase the risk associated with study participation or investigational product administration or may interfere with the interpretation of study results and, in the judgment of the investigator, would make the subject inappropriate for entry into this study.

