7.2. Electrocardiograms

A 12-lead ECG will be obtained from each subject at Weeks 1, 2, 4, 6, 14, 22 and Week 26 and repeated at the follow-up visit if abnormalities were present at the Week 26 (or early termination) visit. Baseline ECG data will be obtained from A1281198 final study visit.

The subject must fast at least 3 hours before ECGs are obtained. ECGs must be obtained prior to the collection of any blood sample because drawing blood can affect the ECG. To standardize the collection procedure, the ECG should be collected in a comfortable and quiet place after the subject has been allowed to rest in a supine position for approximately 5 minutes.

All ECGs must be reviewed for safety at the site by a physician qualified to read and interpret the results (ie, a pediatric cardiologist, or an adult cardiologist experienced in the interpretation of pediatric ECGs should be contacted to discuss the ECG). This assessment will include the calculation of QTcF. ECGs must be reviewed on the day of the recording, signed and dated by the reader, and retained in the subject's study records.

ECGs in this study will be collected with an ECG recorder to be supplied to the site. This machine can generate a hard copy tracing, as well as digitally transmit via a modem to a central ECG service (BMS- BioMedical Systems). Standardized site and subject identification information have to be entered into the machine by the ECG technician prior to each recording. The electronic version transmitted to BMS will be the same as the hard copy. BMS will provide clinical interpretation and overread designated parameters (Heart Rate (HR), PR, Respiration Rate (RR), QRS QT, QTcF, QTcB).

ECGs showing a QTcF of ≥ 480 msec or a suspected increase from baseline of 60 msec or greater must be repeated within the same visit. If the QTcF value persists at ≥ 480 msec and/or the change from baseline persists at ≥ 60 msec, the study drug must be discontinued immediately and a pediatric cardiologist or an adult cardiologist experienced in the interpretation of pediatric ECGs should be contacted to discuss the ECG result.

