9. DATA ANALYSIS/STATISTICAL METHODS

Detailed methodology for summarization of the data collected in this trial will be documented in a Statistical Analysis Plan (SAP). The SAP may modify the plans outlined in the protocol; however, any major modifications of significant change to the primary endpoint definition and/or its analysis will also be reflected in a protocol amendment.

As this is an open label study with no comparator, no inferential statistics will be performed. Quantitative variables will be described by standard descriptive statistics (n, mean, standard deviation, minimum, and maximum, 95% confidence intervals), and qualitative variables will be summarized by frequency tables. Summaries will include data for all subjects who took at least one dose of investigational product in this open label extension study.

Baseline values for efficacy, outcomes and special safety endpoints will be the last observation made prior to the subject receiving open label treatment. For safety, for those subjects who were randomized to placebo in the double blind study, baseline values will be the last (pre dose, for ECG and blood pressure/pulse only) observation prior to initiating dosing in the open label extension study normally, the (pre dose, for ECG and blood pressure/pulse only) observation of the last visit in the double-blind study; and for those subjects who were randomized to ziprasidone in the double blind study, baseline values will be the last observation prior to initiating dosing in the double blind study (normally, the value from the Baseline visit in the double blind study).

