3.4. Baseline Variables

No baseline covariates in the planned analysis.

Baseline visit for the open-label extension study will be the final visit of the double blind trial (Week 4 or early termination visit from A1281198), except for safety ECG parameters. For ECG parameters, baseline values will be the value from the Baseline visit in the double-blind study A1281198.

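### The absolute QTc categories in SAP 6.5.6 are presented as increases but do not require a baseline value below the threshold

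*SAP*

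**What the plan says.** SAP 6.5.6 promises that "the incidence of categorical increases in QTc intervals will be provided" and then defines two families of category.

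- Absolute: "Categories for QTcF and QTcB are ≥ 450 msec, ≥ 480 msec, and ≥ 500 msec". No baseline condition is attached.
- Change: "Categories for QTcF and QTcB as change from baseline are ≥ 30 msec increase", followed by 60 and 75 msec. These are relative to baseline by construction.

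Protocol 9.3 uses the same categories and adds no condition. Neither document defines incidence for ECG findings. By contrast, SAP 6.5.1 does define when an adverse event is treatment emergent relative to the period before open-label dosing.

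At entry, Protocol 4.2 (item 1) excludes subjects "who experienced cardiac arrhythmias, conduction abnormalities, or QTc prolongation" in the preceding study. Prolongation there means confirmed and persistent QTcF above 480 msec, or a QTcF rise above 60 msec. The item sets no limit for QTcB.

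The ECG baseline is defined in three ways:

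- SAP 3.4, for all subjects: "baseline values will be the value from the Baseline visit in the double-blind study A1281198".
- Protocol 7.2: "Baseline ECG data will be obtained from A1281198 final study visit".
- Protocol 9, for subjects randomized to ziprasidone: "baseline values will be the last observation prior to initiating dosing in the double blind study". For subjects randomized to placebo it is the last pre-dose observation before extension dosing.

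**The concern.** An absolute cut-off without a baseline condition measures how many subjects are above the line on treatment. It does not measure how many crossed it. Take an invented example: a child at 455 msec at baseline and 452 msec on drug would enter the 450 msec row of a table of increases, although the interval had shortened by 3 msec.

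In a controlled trial, similar carry-over in each arm would largely cancel in the comparison. Here every subject receives ziprasidone and there is no comparator, so the reader has only the count. Safety is the sole objective (SAP 2.2) and QTc is a named safety endpoint (SAP 3.3). SAP 6.6 also plans to use the safety results of a smaller Chinese-site subgroup in a submission, where each subject carries more weight.

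**Working it through.** The documents state no QTc incidence, precision or prevalence, so there is no figure of the plan's own to reproduce. The check is a reading of the text plus illustrations on stated assumptions.

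**1. Which categories are exposed.** The three change categories already use a baseline, so they are not. Among the absolute categories for QTcF, Protocol 4.2 removes confirmed, persistent values above 480 msec in the preceding study. That leaves mainly the 450 msec category, apart from a value of exactly 480 or one that was not confirmed. For QTcB, no entry limit is stated in item 1, so all three categories are open.

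**2. Weight of one subject.** N = 55 is the expected number eligible (SAP 2.1, Protocol 9.1). 1/55 = 1.8 percentage points in the Combined column, and more in the two group columns and the Chinese subgroup.

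**3. Chance that it happens at all.** P(at least one) = 1 − (1 − p)^55, where p is the proportion at or above 450 msec at baseline. The values of p are assumed.

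| p (assumed) | Expected subjects, 55p | P(at least one) |
|---|---|---|
| 1% | 0.55 | 0.42 |
| 2% | 1.10 | 0.67 |
| 5% | 2.75 | 0.94 |
| 10% | 5.50 | 0.997 |

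**4. Effect on the 450 msec row.** A simulation of 400,000 subjects per scenario, with seven on-treatment visits (Weeks 1, 2, 4, 6, 14, 22 and 26, from Protocol 7.2), one ECG per visit, a 5 msec mean rise on drug, no dropout and no entry exclusion. All QTc inputs are assumed:

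- Scenario A: mean 400 msec; between-subject, between-visit and within-visit SD 15, 10 and 6.
- Scenario B: mean 405; SD 17, 12 and 8.
- Scenario C: mean 410; SD 18, 14 and 10.

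| Scenario | At or above 450 at baseline | Any on-treatment value at or above 450, all subjects | Same, and baseline below 450, over all subjects | Same numerator, over subjects below 450 at baseline |
|---|---|---|---|---|
| A | 0.42% | 4.04% | 3.76% | 3.76/99.58 = 3.78% |
| B | 2.17% | 14.31% | 12.65% | 12.65/97.83 = 12.93% |
| C | 5.34% | 28.52% | 24.23% | 24.23/94.66 = 25.60% |

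Per 55 subjects, the numerator falls by 2.22 − 2.07 = 0.15 in A, 7.87 − 6.96 = 0.91 in B and 15.69 − 13.33 = 2.36 in C. The effect runs from almost nothing to more than two subjects.

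**5. Why the baseline definition matters here.** Suppose a subject on ziprasidone in A1281198 first reached 450 msec during that study. Under SAP 3.4, or Protocol 9 for that group, the baseline precedes ziprasidone and the subject counts as below the threshold at baseline. Under Protocol 7.2, the baseline is taken on ziprasidone and the same subject counts as already above it. Any baseline condition therefore gives different answers until one definition applies.

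**The case against.** The strongest reply is that the text is silent rather than wrong. An incidence of increases can be read as new exceedances only, in which case nothing pre-existing is counted. That reading is available, but nothing in SAP 6.5.6 requires it, and the absolute cut-offs as written suggest a plain count. The reply turns the fault into an ambiguity without removing it.

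Second, the size is unknown. Subjects must also have met the A1281198 entry criteria, which are not in these documents and may restrict QTc further. The study is descriptive, and no decision rule uses these percentages. All of that stands and keeps the point modest.

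Third, Protocol 6.4 records a verified QTcF of 480 msec or more, or a verified rise of 60 msec or more, as an adverse event, and SAP 6.5.1 tabulates and lists those. This protects the serious signals. It does not cover values between 450 and 480 msec, or QTcB.

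A reader might go further and infer that the repeat rule hides real signals. Protocol 7.2 says that an ECG at the QTcF trigger "must be repeated within the same visit", only high readings trigger this, and the SAP does not say which of the two ECGs is used. The documents do not support that inference. They do not say that the repeat replaces the first reading or is averaged with it; taking the larger value would raise the count. Nor does arithmetic show lost signal. Assume a true change of mean 10 and SD 15 msec, and a within-visit SD of 10. The true rate at or above 60 msec is 1 − Φ((60 − 10)/15) = 0.043%, or about 0.17 in 55 × 7 = 385 ECGs with full attendance. First readings reach 60 msec in 0.277% (about 1.07 in 385), and both readings do so in 0.051% (about 0.20). The confirmed count is thus close to the truth, and what disappears on repeat is mostly measurement error. Any-value against confirmed is a trade-off. What remains is a missing detail.

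**Conclusion.** The point holds for the absolute categories. SAP 6.5.6 presents them as increases without requiring a baseline below the threshold, so a pre-treatment value can be counted as an increase. If it is, the 450 msec incidence is overstated as a measure of new exceedances, by 1.8 points per affected subject at n = 55. The number affected cannot be derived from the documents. The probabilities and scenarios above rest on assumed prevalences and SDs, and would shrink if the A1281198 entry criteria already exclude such values.

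Two wider readings should be resisted. It is not true that QTc categories as a whole ignore baseline: the 30, 60 and 75 msec categories are relative to it. And the silence on repeat ECGs does not establish a bias in either direction in the means or the counts. The change is worth making because it uses data already collected and settles the counting rule before the results are seen.

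**What to change.** 1. Reconcile SAP 3.4, Protocol 7.2 and Protocol 9 to one ECG baseline. The change categories depend on it as well.
2. Add a shift table, for QTcF and QTcB separately, from baseline category (below 450, 450 to below 480, 480 to below 500, 500 msec or more) to worst post-baseline category, in the same three columns as the other summaries.
3. For each absolute category, report the incidence among subjects below that threshold at baseline. Keep the all-subject count as a second line, labelled as any on-treatment value.
4. As a minor clarification, state in advance which ECG of a protocol-triggered repeat pair enters the by-visit means, and show any-value and confirmed counts side by side. The trigger reads above 480 msec in note e of the Schedule of Activities but 480 msec or more in Protocol 6.4 and 7.2; these must be reconciled before confirmed counts are defined.

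The cost is one shift table and a few extra rows. No new data are needed.

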6.6. Subgroup analysis

A subgroup analysis of subjects enrolled in Chinese sites will be conducted on the primary, secondary efficacy endpoints, as well as all safety endpoints. The Sponsor plans to utilize the subgroup analysis from both completed pediatric Studies A1281198 and open label study A1281201, to support a submission seeking the indication of the pediatric bipolar disorder for Zeldox in China.

7. INTERIM ANALYSES

No formal interim analysis will be conducted for this study. However, as this is an open-label study, the sponsor may conduct unblinded reviews of the data during the course of the study for the purpose of safety assessment, facilitating dose-escalation decisions, facilitating pharmacokinetic (PK)/pharmacodynamics (PD) modeling, and/or to support clinical development.
